## **8. RESEARCH DESIGN AND METHODS**

### **Overview**

The SMART 2.0 study is a 24-month (96 week) parallel-group randomized control trial designed to evaluate the efficacy of the intervention with technology and personal health coaching or with technology alone to improve objectively measured weight in kg over 24 months compared to a control group. We will recruit 642 overweight/obese young adults aged 18-35 at the University of California, San Diego (UCSD), San Diego State University (SDSU) and California State University, San Marcos (CSUSM) in San Diego. Participants will be assigned to one of three groups for a 24-month study period. The three groups include:

1. SMART 2.0 with technology, social media, and personal health coaching (T1)
2. SMART 2.0 with technology and social media alone (T2)
3. Control group

SMART 2.0 improves upon its predecessor by using a fully integrated system of modalities that includes 1) a popular consumer-level wearable activity tracker (Fitbit Charge 3), wireless scale (Aria Scale), and apps (Fitbit); 2) a highly tailored and interactive text messaging system (described in detail below); 3) multiple social media streams including Facebook, Facebook Messenger, Instagram and Twitter, and 4) enhanced social network mechanisms of influence. Consumer-level devices and apps will be used to self-monitor behavior, and their data will be passively acquired in real-time. Algorithms will be used to automatically deliver interactive text messages to support individually tailored goal setting, performance feedback, and goal review in a highly dynamic style that reflects participants' behavioral progress towards achieving a minimum goal of 5% weight loss. Participants will be encouraged to share their data and behavioral progress with others via social networking tools built into the apps. Social network mechanisms of influence will be used both within the study-space, to elicit participant-to-participant and health coach-to-participant support, as well as outside the study-space, to invoke social support and accountability from strong ties known to be important for long-term behavior change. Additionally, one group will receive monthly technology-mediated, real-time personal health coaching that is theory- and evidence-based.

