**Table 1. Examples of how intervention content will be delivered in SMART 2.0**

Content	Modalities	Description of Delivery
Intention formation and goal setting	Health coaching/ email, SMS, social media/ online groups	

- Health coach will facilitate long- and short-term goal setting with participant during each session followed by an email summary of goals made.

- Activity, dietary, and weight data collected by Fitbit and Aria scale will prompt tailored weekly goals disseminated via SMS.

- Health coach will moderate online group discussion so that each group develops and works toward goals. In turn, the health coach will post social media content tailored toward each groups' goals.

Self-monitoring	Fitbit, Aria scale, SMS, social media	

- Participant monitors physical activity, sleep, and diet with Fitbit and Fitbit app and weight with Aria scale. Ongoing self-monitoring is supported by prompts and reminders via SMS and social media.

Feedback	Health coaching, Fitbit/ Fitbit app, Aria scale, SMS,	

- Health coach will provide feedback on participant's progress toward reaching his/her individual goals.

- Feedback is provided in real time on devices and in Fitbit app.

	social media/online groups	
 
- A data driven automated SMS containing a summary of individual progress toward reaching tailored weekly goals is sent along with a message of encouragement or positive reinforcement.
 
- Participant posts about progress and/or challenges on social media and in online group and receives feedback from their social network, other participants and health coach.
 

Goal review	Health coaching, SMS	
 
- During health coaching sessions, participants will discuss goals and barriers and facilitators for achieving them.
 
- Automated SMS will be sent suggesting a new goal and providing feedback.
 

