## Behavioral Measures

- **Eating Behaviors Inventory (EBI)** will be used to examine eating behaviors and is a widely used self-report assessment of behaviors related to weight loss and weight management (e.g., self-monitoring, refusing offers of food, eating in response to emotions). The measure has been used in over 20 weight

loss interventions. Reliability and validity of the 26-item total score has been demonstrated and the measure has been shown to be sensitive to change in weight management interventions.

- **Physical activity and sleep** will be measured objectively for 10 to 12 days consecutively after each measurement visit using the ActiGraph Link (ActiGraph Inc., Pensacola, FL), a previously validated, wrist-worn and waist-worn tri-axial accelerometer comparable to the device used in National Health and Nutrition Examination Survey. Participants will be asked to wear the device continuously on their non-dominant wrist and around their waist, except while bathing or swimming. The wear location and time period are in-line with the best practices for the assessment of habitual PA and result in high levels of acceptability and compliance among participants (>90%). After each wear period, data will immediately be downloaded and screened for wear time using ActiLife version 6.11.8 or newer (ActiGraph's proprietary software platform). Participants who do not wear the device for a minimum of 10 hours per day on at least 7 days, or who have irregularities in their data indicative of a device malfunction, will be asked to re-wear the device for another period of 10 consecutive days. PA will be defined as cumulative activity “counts” (ActiGraph’s proprietary metric) per day. This metric incorporates intensity, frequency, and duration of acceleration into a single metric and is recommended for assessing the total volume of PA in a 24-hour period. Sleep will be defined as total sleep time, sleep onset latency, wake after sleep onset, and number of awakenings after sleep onset per day determined by an algorithm developed by Cole et al. Participants will also be measured using the Fitbit devices, which provide data on PA (i.e., intensity, energy expenditure, steps, distance traveled, and flights of stairs) and sleep (equivalent to those previously mentioned) at 1-minute epochs, and heart rate at epochs ranging from 1 to 15 seconds.

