### Social Media and Network Connectivity Measures

We will collect participants’ Facebook, Twitter and Instagram data via the application programming interfaces of the respective platforms, if possible according to the rules and regulations of the platforms. We have done this in previous studies, while successfully maintaining participants’ privacy and complying with

requirements from the UCSD institutional review board. These data will allow us to measure the frequency and composition of participants' online communication about healthy-active-living (HAL). Broadcasted posts (e.g., a status update or tweet) that include text will be classified with a dictionary consisting of PA (e.g., swimming) and diet (e.g., fruits) unigrams that was developed by Drs. [name] and [name].

Existing and study-engineered online social network connections (e.g., friends and followers) will be tracked, which will allow for the generation of a number of social network statistics that describe the local structural features (e.g., centrality, tie strength, transitivity) that previous research suggests could be important for health behavior change.

Closest social network connections will be measured by asking participants to name up to 10 of their closest friends regardless of whether they are connected online and respond to 5 questions about the friendship (e.g., "How often do you interact with the friend in real life?"). This measure will be used to determine how real world tie strength may be inferred from easily quantifiable online social network interactions.

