#### Engagement with Intervention Modalities

We acknowledge that the measurement of engagement in the era of digital health is difficult, and throughout the proposed research, we will keep abreast of state-of-the-science methods to accomplish this. Among intervention group participants, quantitative markers of engagement will include usage of Fitbit, SMS sent and replied to, interactions on Facebook and Twitter related to study content (e.g., a post or tweet, like or favorite), website log-ins and click-throughs, emails sent and replied to, and communication with the health coach.

Because this approach does not take into account the depth of interactions (e.g., liking a post is quantitatively the same as writing a post) nor the common practice of lurking (i.e., passively consuming content but not interacting in a visible way), we will also collect qualitative markers of engagement. A previously used questionnaire that includes eight questions (e.g., "In the past week, on average, approximately how many minutes per day have you spent on Facebook?") meant to measure the intensity with which participants use a device or app will be adapted for use in the present study. Importantly, the qualitative markers of engagement will be measured in both the intervention and control groups. These data, combined with the data from online social network connections, will allow us to explore the influence that contamination (i.e., control participants inevitably will use weight-related devices and apps and be connected to and interact with intervention participants on social media) has on intervention effects.

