- **Secondary aim analyses:** Secondary aim 1 will be achieved by using the MMRM approach outlined above to compare differences between the SMART 2.0 intervention groups and the control group at 6, 12, 18, and 24 months in anthropometric and physiological outcomes, PA, diet, sleep, body image, anxiety, depression, and the frequency and composition of participant's online communication about weight-related behaviors (all of these measures are continuous). Secondary aim 2 will examine the dose response (i.e., engagement with intervention modalities) of the SMART 2.0 interventions on outcomes at 6, 12, 18, and 24 months. Engagement variables will be included as independent variables in multiple regression models with the study outcomes as the dependent variable adjusting for covariates. Secondary aim 3 will examine the usability and acceptability of the intervention using the framework advanced by Strauss and Corbin. Transcribed audio recordings will be analyzed in three stages: open, axial, and selective coding. During open coding, the data will be examined line-by-line and key concepts and their properties will be discovered. Axial coding involves identifying the relationships among the data, which will then become fully integrated through selective coding. These processes will be documented via memos, which will provide a roadmap of the analytic process. Secondary aim 4 will be accomplished following methods outlined by MacKinnon and Kraemer. We will examine factors that may mediate or moderate the effect of the SMART 2.0 interventions on study outcomes. Mediators (e.g., PA, diet, social support) will inform how the intervention may have worked to change the outcome, while moderators (e.g., sex, age, social network connectivity, contamination) will illuminate for whom and under what conditions the intervention may have been efficacious. Mediation will be tested via path analysis with regression paths from randomized group to change in the mediator and from change in the mediator to change in the outcome, along with a direct path from the intervention to change in the outcome. Adding interaction terms to the models assessing the intervention effects will test moderation. Secondary aim 5 will examine patterns of PA, diet, and sleep as measured over 24 months by Fitbit and MyFitnessPal using Gaussian process regression models. Models will include separate long- and short-term trends for each of the intervention along with common terms for weekly and yearly periodic trends and indicator variables for holidays. We will also use the time-varying effect model to examine how changes in these behaviors over time influence weight. For all secondary analyses of interest, no adjustments for multiple comparisons will be made and a p-value of 0.05 will be considered statistically significant.

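### In aim 2 the same post can count as both online-communication outcome and engagement dose; in aim 1 the arm difference mixes requested with spontaneous posting

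*Combined protocol and SAP*

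**What the plan says.** All references are to the combined protocol and SAP.

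- **Outcome.** Social Media and Network Connectivity Measures states: "These data will allow us to measure the frequency and composition of participants' online communication about healthy-active-living (HAL". It continues: "Broadcasted posts (e.g., a status update or tweet) that include text will be classified with a dictionary consisting of PA" and diet terms. It gives no counting window, no formula for frequency or composition, and no rule for posts that are prompted, app-generated or about the study.
- **Aim 1.** Under Overall Approach, the secondary aim analyses apply the primary mixed model to a list that ends in "online communication about weight-related behaviors (all of these measures are continuous". Tests are at an unadjusted 0.05, and Section 6 expects secondary differences to favour the intervention groups.
- **What the intervention asks for.** The Overview says: "Participants will be encouraged to share their data and behavioral progress with others via social networking tools built into the apps". Table 1 lists, as a delivery route for feedback: "Participant posts about progress and/or challenges on social media and in online group and receives feedback from their social network". Under Comparison Condition, controls receive only the devices, to use as they wish.
- **Engagement.** Engagement with Intervention Modalities counts, among intervention participants, "interactions on Facebook and Twitter related to study content (e.g., a post or tweet, like or favorite".
- **Aim 2.** Engagement variables are predictors and the study outcomes are responses, with no outcome excepted.
- **A conflicting statement.** Section 14 says that social-media engagement reports on the study's posts are aggregated and that individual participants' engagement is not collected.

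**The concern.** Two things are at stake, both limited to secondary aims.

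In aim 2, the outcome and engagement definitions overlap. If a participant tweets about a study workout, the tweet can raise both the online-communication outcome and the dose marker. Some association then follows from the definitions and would be reported as dose response.

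In aim 1, the treated arms are encouraged to do something that the outcome counts, and the control arm is not. A difference listed beside physiological and psychological outcomes invites the reading that participants came to talk more about health of their own accord. The plan has no analysis that would show whether that is so.

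A smaller matter is the statement that every listed measure is continuous. It is wrong for post frequency, which is a count.

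**Working it through.** **The plan's own figure.** No power, rate or SD is given for online communication. The only sample-size figure is for weight: difference 1.60 kg, SD 4.92 kg, two-sided 2.5%, 80% power. The standardised effect is 1.60/4.92 = 0.325. The noncentral-t calculation gives 182 per group with power 80.2%, as stated. I use 182 per group below.

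**Aim 2.** Within the intervention arms, write

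- outcome Y = S + P, where S is spontaneous weight-related broadcast posts and P is broadcast posts on study content that contain dictionary words;
- engagement E = P + L, where L is likes and other interactions.

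Then Cov(Y, E) = Var(P) + Cov(S, P) + Cov(S, L) + Cov(P, L). If S, P and L are all unrelated, Cov(Y, E) = Var(P), which is positive whenever participants differ in P. The association is therefore partly built in. How large it is depends on the share of P in each variable, which the documents do not give.

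**Aim 1.** If controls make essentially no study-content posts, the expected arm difference is [mean S (treated) − mean S (control)] + mean P (treated). One observed difference cannot identify both parts.

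**How easily P alone reaches significance.** With 182 per group and two-sided 0.05, the shift detectable with 80% power is (1.96 + 0.84) × √(2/182) = 0.29 SD. The inputs below are assumptions, not figures from the documents: negative binomial unprompted counts, the same in both arms; Poisson requested posts added in one arm; a t-test at one visit; 10,000 simulated trials per row.

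| Mean posts | Dispersion | Zeros | SD | Significant, none added | One added | Two added |
|---|---|---|---|---|---|---|
| 2 | 0.3 | 54% | 3.92 | 4.9% | 68.5% | 99.5% |
| 2 | 1.0 | 33% | 2.45 | 4.5% | 96.2% | 100% |
| 5 | 0.3 | 42% | 9.40 | 4.6% | 18.2% | 53.3% |
| 5 | 1.0 | 17% | 5.48 | 5.1% | 40.8% | 92.6% |
| 10 | 0.3 | 35% | 18.53 | 4.8% | 8.3% | 18.3% |
| 10 | 1.0 | 9% | 10.49 | 5.1% | 14.9% | 44.5% |

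The ordering follows the 0.29 SD threshold: one added post is 1/2.45 = 0.41 SD in the second row and 1/18.53 = 0.05 SD in the fifth.

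**Count against continuous.** With none added, rejection is 4.5% to 5.1%, so treating the counts as continuous does not inflate type I error here. A separate simulation (gamma-Poisson, mean 4, shape 0.5, 182 per arm, 1,500 trials) compared least squares on change with a negative binomial model. Rejection was 4.9% against 5.1% at a rate ratio of 1.0, and 75.5% against 78.7% at 1.4, a gain of 3.2 points.

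**The case against.** The strongest reply is that the overlap is narrower than it looks.

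- The plainest request to interact concerns the online groups, which run in private Messenger threads and are not evidently broadcast posts.
- Sharing through tools inside the apps need not reach Facebook, Twitter or Instagram.
- Engagement includes likes and covers study content only.
- Section 14 says individual engagement is not collected.

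All this stands against reading the outcome and the dose as the same posts. It does not remove the overlap. Table 1 names social media separately from the online group, and a tweet on study content meets both definitions. Section 14 contradicts the engagement section and the aim 2 regressions rather than settling the matter.

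The second reply concerns interpretation. A reader might infer that a favourable arm difference shows adherence rather than effect. The documents do not support that. The randomised comparison validly estimates the total effect of assignment, and support from existing networks is an intended mechanism (Overview; Section 7 reports such talk in the predecessor trial). Physical activity and sleep are also prescribed, and nobody would dismiss those outcomes as mere adherence.

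Third, Overall Approach already provides for transformation and non-parametric alternatives, and the simulated gain from a count model is small. This stands: the scale statement is an error of description with little shown consequence.

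Finally, deleting study-related posts from the main comparison would remove content after randomisation, mostly from the treated arms. If requested posts replace spontaneous ones, the contrast would be biased downward. This also stands, so such a filter belongs in a sensitivity analysis.

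**Conclusion.** The point holds as a minor one, for one secondary outcome and its use in aim 2. As written, aim 2 permits a partly mechanical association between post-based engagement and online communication. In aim 1 the arm difference is valid as a total effect but cannot be split into requested and spontaneous posting. The size is unknown because the documents give no posting rates; the 8% to 96% range shows only that requested posts alone could be enough. It rests on the assumed counts and on a one-visit t-test simpler than the planned mixed model. The reading also assumes that the encouragement to share in the Overview is meant for the intervention arms; the sentence does not name them, but it sits in the description of the SMART 2.0 system.

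Two further inferences should not be drawn. Composition is never defined, so the documents do not show that it is a ratio or that it is missing for any given share of participants. The scale error should not be extended to the sleep measure "number of awakenings after sleep onset per day": expressed per day over a wear period of 10 to 12 days, it is ordinarily analysed as a mean rate. The primary weight analysis is untouched.

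**What to change.** 1. **Aim 2.** State that post-based social-media engagement will not be used as a predictor of online communication. Other engagement markers and other outcomes stay as planned.
2. **Engagement data.** Reconcile Section 14 with Engagement with Intervention Modalities and the aim 2 text, so that it is clear which individual-level social-media data will exist.
3. **Aim 1.** Keep the comparison on all posts, but label it a process measure: the total effect of assignment, including requested posting. Add a sensitivity analysis that sets aside identifiable study-related or app-generated posts, and say that it conditions on content arising after randomisation.
4. **Scale.** Correct the statement that all the measures are continuous, since post frequency is a count, and state the counting window and what composition means. A count model is optional.

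The cost is one aim 2 model lost, some SAP wording and a modest extra analysis. The activity and diet word dictionary cannot by itself recognise prompted posts, so the sensitivity analysis needs a simple additional marker and will catch only posts that can be identified. The rules should be fixed before any data are examined by arm.

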- Diet will be measured for 3 days (2 weekdays and 1 weekend day) after each measurement visit using the **Automated Self-administered 24-hour Dietary Recall (ASA24)**, a previously validated web-based tool developed by the National Cancer Institute. The ASA24 prompts individuals to recall, in detail, for each meal and snack, the foods and beverages they have consumed during the previous 24-hour period. The program calculates kcal and macronutrients (e.g., fats, protein, carbohydrates), as well as 90 micronutrients (i.e., vitamins and minerals), food groups (e.g., grains, vegetables), and other dietary constituents (e.g., added sugars). It also facilitates the calculation of the Healthy Eating Index, a measure of diet quality that can be used to assess compliance with the Dietary Guidelines for Americans. ASA24 data will be collected via computer through HTML screen and directly formatted and stored in tables on the study’s REDcap database.
- The **Global Physical Activity Questionnaire (GPAQ) and Paffenbarger Exercise Habits Questionnaire** will be the methods used to estimate physical activity. The GPAQ was developed by the World Health Organization. The Paffenbarger was developed for the Harvard Alumni Study to assess leisure-time physical behavior. The time reference for the GPAQ will be “in a typical week”. The time reference for the Paffenbarger will be “in the past week”. GPAQ and Paffenbarger data will be collected via survey through the study’s REDcap secure database.
- **Sedentary behaviors** will be measured with the Last 7 Day Sedentary Behavior Questionnaire (SIT-Q-7d), which was developed and validated by [name] and colleagues. The SIT-Q-7d assesses sitting or lying down in five domains (meals, transportation, occupation, non-occupational screen time, and other sedentary time), thus facilitating the calculation of domain-specific and total sedentary time. Strategies for weight management will be measured with a 35-item questionnaire that assesses the frequency of using evidence-based strategies to achieve decreased energy intake and increased energy expenditure for weight management (e.g., “Recorded or graphed my weight”). Frequency within the last 30 days is assessed on a 5-point response scale, ranging from “never or hardly ever” to “always or almost always”.

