### **Overall Approach**

Analyses will be conducted using the latest version of the statistical software platform R and will be based on the intention-to-treat principle. All tests of significance will be two-sided and a p-value of 0.05 will be considered statistically significant. Summary statistics (e.g., mean, standard deviations, proportions) will be calculated for all variables of interest. Outliers will be assessed and variables whose distributions depart significantly from normality will be transformed. Appropriate non-parametric alternatives will be considered if parametric assumptions fail. No planned interim analyses for efficacy or futility will be conducted in this study.

- **Primary aim analysis:** The primary outcome of the study is change in objectively measured weight in kg, and the SMART 2.0 intervention groups will be compared to the control group using a mixed model of repeated measures (MMRM). The model will include change in weight from baseline at each post-baseline visit (i.e., 6, 12, 18, and 24 months) as the dependent variable. Fixed effects will include study group, visit, study group-by-visit interaction, weight at baseline, and any variables determined to be confounders. Visit will be treated as a categorical variable, and an unstructured variance-covariance structure will be used. Results will be reported as point estimates (mean differences between groups) and

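### The aim 4 mediation model lists no baseline covariates, so its non-randomized mediator-to-weight path is open to confounding in a direction that cannot be stated in advance

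*Combined protocol and SAP*

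**What the plan says.** Section 8, Overall Approach, gives the aim 4 model within the secondary aim analyses. The path model for mediation has "regression paths from randomized group to change in the mediator and from change in the mediator to change in the outcome". A third path completes the model, described as "along with a direct path from the intervention to change in the outcome". No covariate, confounder set or sensitivity analysis follows. The aim as a whole "will be accomplished following methods outlined by" the authors of two cited methods papers. Its purpose is explanatory: "Mediators (e.g., PA, diet, social support) will inform how the intervention may have worked to change the outcome".

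The same section states adjustment in two other places. Aim 2 uses "multiple regression models with the study outcomes as the dependent variable adjusting for covariates". The fixed effects of the primary MMRM, which aim 1 reuses, include "study group-by-visit interaction, weight at baseline, and any variables determined to be confounders".

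Aim 4 offers diet as an example of a mediator without naming the diet variable. The Behavioral Measures section has a web-based dietary recall (ASA24): "Diet will be measured for 3 days (2 weekdays and 1 weekend day) after each measurement visit". It also has the Eating Behaviors Inventory, which "will be used to examine eating behaviors and is a widely used self-report assessment". Table 7 lists continuous device- and app-based diet data as well.

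**The concern.** Participants are randomized to a group, not to a change in activity or diet. Those who change these behaviors may differ at baseline from those who do not, for example in weight, habitual activity and diet, sex or age. The same characteristics may predict weight change. Working with change scores removes stable additive differences between people. It does not remove a baseline characteristic that predicts how much someone changes.

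At stake is the explanation of the result. The trial has one arm with coaching plus technology and one with technology alone. A biased mediator-to-weight path moves effect between the behavioral route and the direct route in each comparison with control. Secondary analyses are tested at 0.05 without multiplicity adjustment, so no tighter threshold offsets a spurious path.

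A second, narrower matter concerns diet. If the recall is the mediator, its change score carries the day-to-day noise of two 3-day samples, and the written model has no step to deal with it.

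**Working it through.** **The plan's own figures.** The plan gives no number for mediation: no reliability, no mediated share, no power. Its sample size supplies the n used here. With an SD of 4.92 kg, a difference of 1.60 kg, two-sided alpha 0.025 and 80% power, the exact t-test needs 181.01, so 182 per group, as stated. Then 182/0.85 = 214.1, and 3 x 214 = 642. The number analysed is 3 x 182 = 546 (0.85 x 642 = 545.7).

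**1. Confounding of the mediator-to-weight path.** Assume no true mediator effect and one baseline cause with correlation r to both the mediator change and the weight change. The documents give no value for r; 0.2-0.4 is an assumption. The spurious correlation is r x r. The test statistic is centred near atanh(r²) x √546, with √546 = 23.37, and is compared with 1.96:

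| r | r² | centre | rejection rate, formula | rejection rate, simulation |
|---|---|---|---|---|
| 0.2 | 0.04 | 0.93 | 15% | 15-16% |
| 0.3 | 0.09 | 2.11 | 56% | 53-56% |
| 0.4 | 0.16 | 3.77 | 96% | 96% |

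The simulations used 2,000 to 4,000 trials per setting. Adding the baseline cause as a covariate brought all three rates back to about 5%.

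**2. From one path to a mediation claim.** A joint-significance test also needs the group-to-mediator path.

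- With no group effect on the mediator that path is significant 5% of the time. The joint rate is 0.05 x (0.15, 0.56, 0.96), about 1%, 3% and 5%.
- With an assumed group effect of 0.2 SD and 182 per arm, the statistic is centred at 0.2/√(2/182) = 1.91, which gives power of about 48%. The joint rate is 0.48 x (0.15, 0.56, 0.96), about 7%, 27% and 46%.

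**3. If r refers to true rather than measured change.** With reliability λ the spurious correlation becomes r²√λ. For λ of 0.38-0.64 the single-path rates fall to about 9-12%, 25-39% and 63-85%.

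**4. Reliability of a change in the 3-day recall.** Assume a within- to between-person variance ratio of 1-2 and a correlation ρ of true intake between visits of 0.4-0.6. Neither is in the documents.

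λ = (1 − ρ) / ((1 − ρ) + ratio/3)

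- Ratio 1, ρ 0.4: 0.6/(0.6 + 0.333) = 0.64.
- Ratio 2, ρ 0.6: 0.4/(0.4 + 0.667) = 0.375, about 0.38.

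Random error alone would leave 38-64% of the diet-mediated effect in the indirect path and move the rest to the direct path. A wider set of assumptions (single-day intraclass correlation 0.2-0.5, true correlation 0.3-0.7) gives λ of 0.18-0.68.

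**5. Net direction.** In large samples, estimated indirect effect / true indirect effect = λ(1 + k)(1 + d). Here k is the relative confounding bias of the mediator-to-weight path and d is differential reporting by arm. Suppose the true indirect effect is 50% of the total, λ = 0.6 and d = 0. The estimate is then 15%, 30%, 45% or 60% for k = −0.5, 0, 0.5 or 1. It exceeds the truth once k is above 1/0.6 − 1 = 0.67. Across all scenarios run (λ 0.4-0.8, k −0.5 to 1, d 0 or 0.5) it ranged from about 10% to over 100%.

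**6. Covariates without an error correction.** With λ = 0.6 and a confounder explaining a quarter of the variance in mediator change, adjustment leaves a conditional reliability of 0.75/(0.75 + 0.667) = 0.53. The estimate is then about 27% against a true 50%.

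**The case against.** The strongest reply is that the text is silent rather than wrong. It sketches the structural paths and defers to two methods papers that are not available here and may call for covariates. A reader might infer that the plan rules covariates out; it does not. What remains is that a citation cannot say which covariates this trial will use, and that the same section does state adjustment for other aims.

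A reader might also infer that the plan treats a 3-day recall as error-free and so understates the role of diet. The documents do not support that. Aim 4 does not name the recall as its diet variable, and other eating and diet data are collected. Even with the recall, step 5 shows that confounding can offset or outweigh the attenuation. The plan also promises no mediated share, only a test.

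Nor can the noise argument be extended to every mediator. Activity is recorded for 10 to 12 days, with re-wear requested when there are fewer than 7 adequate days. The step 4 formula, with the same assumed inputs, then gives 0.58-0.81 at 7 days and 0.67-0.86 at 10. Social support is measured by questionnaire, so a latent variable built from separate days cannot apply to it. For diet, such a model is one option among several.

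Finally, the 15-96% range could be read as a rate of false mediation findings. It is the rate for one path; step 2 gives the lower joint rates. These objections limit the size and direction of the problem. They do not supply the missing adjustment set.

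**Conclusion.** The point holds as a gap in the aim 4 model. Run as written, the mediator-to-weight path is unadjusted, and randomization does not protect it. The indirect effect is open to confounding by baseline characteristics, with no predictable direction.

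The size rests on assumptions. For correlations of 0.2-0.4, which the documents do not give, the false-positive rate of that path is about 15-96% at n = 546. A joint mediation test with a 0.2 SD group effect on the mediator gives about 7-46%. Attenuation by a factor of about 0.38-0.64 is conditional on the 3-day recall being the diet mediator, on the assumed variance inputs, and on error that is random and unrelated to arm. It describes the error component only, not the net bias.

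Aim 4 is secondary, and the 24-month MMRM comparison does not depend on it. The change is still worth making before analysis, because it costs little and this aim is the one meant to explain how the intervention worked.

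**What to change.** In section 8, Overall Approach, aim 4:

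1. Add the baseline value of the mediator, baseline weight, sex, age and campus to both the mediator equation and the outcome equation. Weight, sex, age, activity and diet are recorded at baseline under the measures sections and Table 7, and campus is known from eligibility. The Background section reports that the predecessor trial's weight analysis adjusted for sex and college, so there is precedent. Table 7 does not list the social support surveys, so confirm that a baseline value exists for that mediator.
2. Report a sensitivity analysis for unmeasured mediator-outcome confounding, for example the residual correlation between the two equations at which the indirect effect would vanish.
3. State which diet variable is the mediator. If it is the ASA24 recall, add a reliability-corrected sensitivity analysis for that mediator only, using the separate recall days. Note that two weekdays and one weekend day are not interchangeable replicates, and that the correction does not remove systematic or arm-dependent misreporting. As step 6 of the working shows, the covariates do not do this job.

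The cost is plan wording and slightly more analysis work, with no new data for activity or diet. The error-corrected estimate will have a wider interval.
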